**Proprietary confidential information.**

© 2015 Boehringer Ingelheim International GmbH or one or more of its affiliated companies. All rights reserved.

This document may not - in full or in part - be passed on, reproduced, published or otherwise used without prior written permission.

Approximately half of the patients participating in this trial may derive a direct benefit from being treated with an active compound and not a placebo. Patients who are not adequately controlled (whether in the blinded placebo or active compound group), as evidenced by FPG or blood glucose values (by HBGM device), will have adjustments to their background therapy or receive rescue therapy (according to [Section 4.2.1](#)) to ensure their safety.

Rescue therapy will be permitted in case of hyperglycaemia during the randomised treatment period if the defined criteria are met (refer to Section 4.2.1). The choice of rescue medication and its dosage according to Section 4.2.1 will be left to the discretion of the investigator and rescue medication will be taken in accordance with the local prescribing information of that respective medication. The use of rescue medication may be associated with relevant side effects, such as increase of hypoglycaemia risk, weight gain, etc.

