### 7.4 HANDLING OF MISSING DATA

#### 7.4.1 Efficacy endpoints

In the primary analysis, if a patient misses a visit, the missing data will not be imputed. The mixed effect model will handle missing data based on a likelihood method under the "missing at random assumption". Following the intention-to-treat (ITT) principle, every randomised patient with at least baseline and one on-treatment measurement will be included in the analysis.

If rescue therapy is initiated, HbA1c and FPG values after rescue will be set to missing and the missing data handled as above (OC or LOCF), according to the analysis strategy.

**For the analysis of hypoglycaemia endpoints, the available data of all patients in the TS will be analysed (OC approach) and no imputation performed.**

For binary endpoints including an HbA1c response criterion, non-completer's considered failures (NCF) approach will be used, i.e., patients who discontinue from the trial prematurely and have no Week 24 HbA1c value will be considered as non-responders.

Methods to handle any other exceptional cases will be considered before unblinding the data and will be applied in a manner consistent with other trials of this type. The evaluability of patients with deviations from the protocol likely to confound the treatment response will be decided prior to unblinding.

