6.6 HANDLING OF MISSING DATA AND OUTLIERS

Patients may drop out of the trial before they reach the planned observation time. In particular, patients with a lack of efficacy can be expected to drop out with a higher probability than patients showing a good response. Therefore various methods will be used to assess the

impact of missing data on the efficacy endpoints of the trial. The following paragraphs give a general description of the various approaches.

Original Results (OR) analysis

For some of the efficacy endpoints, analysis will be done directly on the observed data, without any derivation performed on them. OR analysis is relevant in cases rescue therapy was taken.

Observed cases (OC)

One general approach that is possible for all endpoints is to analyse only the available data that were observed while patients were on treatment, i.e. excluding the missing data. Missing data in this analysis will not be replaced.

For all efficacy endpoints using OC, this OC-technique will be adapted by setting any values taken after rescue medication to missing. In addition values after the addition of a new anti-diabetic therapy or an increase in metformin and/or AGI dose as specified in [Section 5.3](#) will be set to missing.

It should be noted that this method provides unbiased estimates only under the assumption that the data are missing at random; and so, this method is likely to lead to non-conservative estimates of the treatment effects in case of data missing due to patients dropping – out because of lack of efficacy of the study medication under treatment.

Observed cases – Rescue observed cases (OC-ROC)

In this case, values taken after rescue medication are neither set to missing nor are imputed otherwise but taken as measured.

Last observation carried forward (LOCF)

An alternative method for quantitative endpoints is to replace missing values due to early discontinuation of a patient by her/his last observed measurement on treatment. This method tends to result in more conservative estimates than an OC-analysis.

The last observation on-treatment must not necessarily be a value selected as a visit value as described in [Section 6.7](#). If multiple measurements were performed within a time window for a visit, the last on-treatment value within the time window will be carried forward, while the visit value can be the value that was observed closest to date of last drug administration or the first value observed in the time window.

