OR	Continuous, binary, time to event and count	No imputation	All data included as measured. Multiple measurements per visit possible.
OC	Continuous	No imputation	Excluded – considered missing. One picked value per visit (cf. Section 6.7).
OC-ROC	Continuous, binary, time to event and count	No imputation	Included as measured. One picked value per visit (cf. Section 6.7).
LOCF	HbA _{1c} (at each visit and change from baseline)	Missing values at the end of the trial are replaced by the last on-treatment value. Missing values with subsequent present on-treatment values are imputed by interpolation. Baseline values are not carried forward, except where rescue medication is taken prior to first on-treatment measurement. Baseline values can be used in interpolation.	Values after the start of rescue therapy are replaced by the last available measurement. If no on-treatment HbA _{1c} measurement prior to rescue therapy is available baseline values are carried forward.
MI	HbA _{1c}	Missing values are imputed by a two-step approach. Firstly, a monotone missing pattern is generated in the data (MCMC method). Secondly, missing values are imputed by a sequential regression based method.	Considered missing and thus imputed.

Table 6.6: 1 Summary of imputation methods for efficacy endpoints (cont.)

Imputation method	Endpoint	Handling of missing values	Handling of values after rescue therapy
NCF	Binary endpoints derived from continuous endpoints (e.g. HbA _{1c} <7.0%)	Missing values after premature discontinuation of trial medication are considered failure (endpoint not achieved). Missing values with subsequent present on-treatment values will be imputed based on the interpolated values for the underlying continuous endpoint.	Values after the start of rescue therapy are imputed as failure.

[REDACTED]

[REDACTED]

Safety and other variables

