6.7 BASELINE, TIME WINDOWS AND CALCULATED VISITS

Definition of baseline

With regard to efficacy and safety endpoints, the term "baseline" generally refers to the last observed measurement prior to administration of any randomised study medication. Baseline daily basal insulin dose is derived from eCRF and is equal to the daily basal insulin dose at day of first study medication intake. If patients are treated by a combination of a fast-acting and basal insulin, only the proportion of basal insulin is used for deriving the baseline daily basal insulin dose. If that proportion cannot be derived, baseline daily basal insulin is set to missing.

If patients are treated with an intermediate type of insulin, then this dose is completely considered for daily basal dose.

Also, for metformin and AGI, baseline doses refer to the dose at day of first study medication intake.

Measurements taken prior to the first intake of randomised trial medication will be considered pre-treatment values. These pre-treatment values will be assigned to a visit according to the nominal visit number as recorded on the eCRF or as provided by the laboratory.

The date and clock time of the first study medication administration will be used to separate pre-treatment from on-treatment values.

The definition of screening for the analysis of concomitant therapies (CTs) is the time period from informed consent up to the first dose of trial medication.

Definition of on-treatment for analyses

Measurements taken after the first intake of randomised study medication will be considered on-treatment values if they have been obtained up to 7 days after study medication stop (inclusive) – this also holds for hypoglycaemia (efficacy endpoints) and hypoglycaemic adverse events (safety endpoints). The only exceptions are FPG [REDACTED] for which will be up to 1 day after drug stop (inclusive) due to reacting quicker. All on-treatment measurements will be assigned to the randomised trial medication for analyses.

Measurements taken after the end of the follow-up period after the last intake of trial medication will be considered post-trial values.

Visit windows for efficacy variables

On-treatment efficacy measurements will be assigned to visits based on time windows around the planned visit dates. These time windows are defined based on the planned number of days after the date of first administration of trial medication (this is at Visit 3).

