Repeated and unscheduled efficacy measurements will be assigned to the nominal visits and listed in the subject data listings according to the time windows described above. Only one observation per time window (visit value / picked value) will be selected for analysis at an on-treatment visit – the value will be selected which is closest to the protocol planned visit day; except for last study drug intake. In case of last study drug intake, the value which is closest to the date of last study drug intake is chosen. If there are two observations which have the same difference in days to the planned day or if there are two observations on the same day, the earliest value will be used. If an observation is available on the last day of treatment, this observation will be preferably selected over any later observation that is still within the time window. If there are multiple values within the time window of the last visit,

including a value on the last day of drug intake, the value on the last day of drug intake is used as the value of the last visit.

Note: For LOCF imputation, the last observed on-treatment value will be carried forward, whether or not it was selected in the previous time window. Also for interpolation any valid values can be used, regardless of whether they were selected as visit values. For more details on LOCF refer to [Section 6.6](#).

For daily basal insulin the value at the visit will be determined as the last prescribed dose prior to the picked HbA1c value of the visit.

Visit windows will not be applied to hypoglycaemia or use of rescue therapy and events will not be assigned to visits. All on-treatment events will be considered in the analysis.

Visit windows for safety variables

Safety measurements will be assigned to the nominal visit as recorded on the eCRF or as provided by the laboratory. In general, visit windows will not be applied. However, for the Week 24 analysis, if a Japanese patient stops drug intake prior or at day 175 a residual period of 7 days will be added for safety analysis. If a Japanese patient does not stop drug intake prior day 176, no residual period is added for safety analysis at Week 24.

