7.5.2 Secondary endpoints

Proportion of patients with at least one hypoglycaemia accompanied by a glucose value during 24 weeks of treatment

Logistic regression for the proportion of patients experiencing at least one hypoglycaemia after 24 weeks will be performed on the FAS (OC); all on-treatment hypoglycaemias will be considered:

- up to drug stop date if a patient prematurely discontinues (Japanese patients that prematurely discontinue prior or at day 175)

- up to trial medication stop date – 1 if a non-Japanese patient does not prematurely discontinue
- up to day 175 if a Japanese patient does not prematurely discontinue prior day 176.

The model will include *treatment* as fixed effect and *baseline HbA_{1c}* and *baseline daily basal insulin dose* as linear covariates.

Frequencies regarding the number and percentage of patients experiencing at least one hypoglycaemia accompanied by a glucose value during 24 weeks in each treatment group will also be presented based on FAS(OC) .

Proportion of patients with HbA_{1c} on treatment <8.0% after 24 weeks of treatment

Logistic regression for the patients achieving HbA_{1c} <8.0% at Week 24 will be performed on FAS (NCF); patients who do not complete 24 weeks of treatment will be considered non-responders. The model will include *treatment* as fixed effect and *baseline HbA_{1c}* and *baseline daily basal insulin dose* as linear covariates. Patients with baseline HbA_{1c} <8.0% will be excluded from the analysis.

A frequency table with the number and percentage of patients with HbA_{1c} <8.0% at Week 24 in each treatment group will be also be presented based on FAS (NCF).

Proportion of patients with HbA_{1c} on treatment <7.0% after 24 weeks of treatment

Logistic regression for the patients achieving HbA_{1c} <7.0% at Week 24 will be performed on FAS (NCF); patients who do not complete 24 weeks of treatment will be considered non-responders. The model will include *treatment* as fixed effect and *baseline HbA_{1c}* and *baseline daily basal insulin dose* as linear covariates. Patients with baseline HbA_{1c} <7.0% will be excluded from the analysis.

Frequencies regarding the number and percentage of patients with HbA_{1c} <7.0% at Week 24 in each treatment group will be also be presented based on FAS (NCF).

Proportion of patients with HbA_{1c} lowering by at least 0.5% after 24 weeks of treatment

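### The SAP's observed-cases rule, read literally, deletes post-rescue hypoglycaemia events that the rest of the plan indicates should count

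*SAP*

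**What the plan says.** **General rule.** In SAP 6.6, the paragraph on observed cases (OC) reads: "For all efficacy endpoints using OC, this OC-technique will be adapted by setting any values taken after rescue medication to missing". No exemption for hypoglycaemia is visible.

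**The endpoint.** SAP 6.7 places hypoglycaemia among the efficacy endpoints when it extends the on-treatment definition: "this also holds for hypoglycaemia (efficacy endpoints) and hypoglycaemic adverse events (safety endpoints". SAP 7.5.2 specifies that the logistic regression "will be performed on the FAS (OC); all on-treatment hypoglycaemias will be considered". The cut-offs that follow depend on drug stop or day 175, not on rescue. SAP 6.7 adds that visit windows do not apply to hypoglycaemia and that "All on-treatment events will be considered in the analysis".

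**The table.** Table 6.6: 1 lists OC for continuous endpoints only, with post-rescue data "Excluded – considered missing. One picked value per visit". Two rows cover binary endpoints and keep post-rescue data. They are OC-ROC ("Included as measured. One picked value per visit") and OR, which uses all data as measured and allows several measurements per visit.

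**The protocol.** Protocol 7.4.1 confines post-rescue deletion to two laboratory measures, HbA1c and FPG: "FPG values after rescue will be set to missing and the missing data handled as above". For hypoglycaemia it analyses the available data of all treated patients without imputation, and calls this an OC approach. Protocol 2.2 makes a reduction in hypoglycaemia risk something the trial will assess. Protocol 2.3 warns: "The use of rescue medication may be associated with relevant side effects, such as increase of hypoglycaemia risk, weight gain, etc".

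**The concern.** The 6.6 rule has two conditions: the endpoint is an efficacy endpoint, and it is analysed as OC. The hypoglycaemia endpoint meets both. A programmer who applies the SAP's own definition of OC would delete events after rescue. One who follows the rest of the 7.5.2 sentence would keep them. The two datasets differ whenever a rescued patient's first qualifying event comes after rescue.

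This matters because rescue is not neutral for this outcome. Under Protocol 4.2.1, rescue includes sustained basal insulin increases above set limits and new antidiabetic agents, and the protocol itself says rescue may raise hypoglycaemia risk. If the drug lowers glucose, more rescue on placebo is plausible, although the documents do not say so. Deletion would then remove more events from placebo than from linagliptin. The handling should be settled in the text before unblinding.

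**Working it through.** **1. The plan's own figure.** The only power figure is for HbA1c: 150 per arm, difference 0.77, SD 1.2, two-sided 5%, stated power above 99% (Protocol 7.6). The standardised difference is 0.77 / (1.2 × √(2/150)) = 5.56, and Φ(5.56 − 1.96) = 0.9998, so the figure reproduces. The present point does not depend on it. No power figure is given for hypoglycaemia.

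**2. Which texts govern post-rescue events?**

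| Text | Post-rescue hypoglycaemia |
|---|---|
| SAP 6.6, OC paragraph | Deleted, if read literally |
| SAP 7.5.2, cut-offs | Counted; only drug stop or day 175 ends counting |
| SAP 6.7 | Counted; all on-treatment events |
| Table 6.6: 1 | OC not defined for binary endpoints; OR and OC-ROC keep the data |
| Protocol 7.4.1 | Not deleted; the rule names HbA1c and FPG only |

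One general sentence stands against four other texts. What remains is a label in 7.5.2 that triggers the wrong rule.

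**3. Illustration of what literal deletion could do.** All rates here are assumptions, because the documents give none. With all on-treatment events counted, take 30% on placebo (45/150) and 20% on linagliptin (30/150), unadjusted.

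- OR = (30/120) / (45/105) = 0.583, so ln OR = −0.539
- SE = √(1/45 + 1/105 + 1/30 + 1/120) = 0.271
- z = 1.99, p = 0.047

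Let r be the share rescued in an arm and f the share of rescued patients whose only event follows rescue. If deletion makes those patients event-free, the arm's risk becomes p − r·f. For example, with rescue 10% on placebo and 5% on linagliptin and f = 0.3, the risks are 0.30 − 0.03 = 0.27 and 0.20 − 0.015 = 0.185. The OR is (0.185/0.815) / (0.27/0.73) = 0.614, p = 0.081.

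| Rescue, placebo / linagliptin | f = 0.1 | f = 0.3 | f = 0.5 |
|---|---|---|---|
| 5% / 5% | 0.579, p = 0.045 | 0.569, p = 0.042 | 0.559, p = 0.039 |
| 10% / 5% | 0.593, p = 0.056 | 0.614, p = 0.081 | 0.636, p = 0.114 |
| 20% / 10% | 0.603, p = 0.067 | 0.649, p = 0.135 | 0.706, p = 0.256 |

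Starting instead from 30% in both arms, deletion with 20% / 10% rescue gives ORs of 1.05 to 1.33.

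**4. Coding.** SAP 6.6 says values are set to missing. It does not say whether a yes/no outcome then becomes event-free or missing. If the affected patients are dropped instead, the non-event counts stay at 105 and 120. The most extreme cell (20% / 10%, f = 0.5) becomes (22.5/120) / (30/105) = 0.656, p = 0.17. The direction is the same and the shift is smaller.

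**The case against.** The strongest reply is that intent is clear. SAP 6.6 presents its methods as general descriptions. The endpoint-specific text in 7.5.2 and 6.7 is explicit and should prevail, and the OC label probably descends from Protocol 7.4.1, where it means available data without imputation. This largely stands: the readings are not equally supported, and nothing specific to hypoglycaemia favours deletion. It does not remove the problem, because the SAP redefined OC to include deletion and then attached that label to this endpoint.

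The cross-referenced SAP 5.3 and other parts are not visible, and a clarification may be there. That also stands and limits how firmly the point can be put.

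Two stronger readings are tempting. A reader might infer that the sponsor intends to delete events, or that the objective has two equally valid answers. The texts above do not support either.

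A reader might also infer that counting post-rescue events manufactures a large spurious benefit. Assume 30% background risk in both arms, rescue 5% on linagliptin and 10–20% on placebo, 70% of rescued patients event-free at rescue, and 20–50% of those having a first event afterwards. Simple addition gives differences of 0.7 to 5.2 points. That double-counts, because rescued patients would have had some of those events anyway. With constant hazard and rescue at week 12, √0.70 = 84% are event-free at rescue and 16% of those have a first event regardless. The excess is then 0.05 × 0.84 × (0.20 − 0.16) to 0.15 × 0.84 × (0.50 − 0.16), which from unrounded values is about 0.15 to 4.2 points. The chance of p < 0.05 is at most about 12%. This is a reason for a sensitivity analysis, not for deletion.

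**Conclusion.** The point holds as an error in the SAP's general rule and label. The 6.6 sentence is wrong for the hypoglycaemia endpoint, and the plan's other texts indicate that post-rescue events count. On the assumed rates, literal deletion is trivial if rescue is rare or equal between arms, but can carry a borderline p-value across 0.05 if rescue differs by arm. None of those rates comes from the documents, so the size is illustrative only. The primary HbA1c analysis is unaffected. SAP 5.2.1 names no key secondary endpoint, although Protocol 7.1 still places hypoglycaemia after the primary in a hierarchy. It is worth correcting because the endpoint serves a stated objective and the correction is cheap.

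**What to change.** 1. In SAP 6.6, limit the post-rescue deletion under OC to continuous endpoints (HbA1c, FPG), after checking any endpoints not visible in the public version.
2. In SAP 7.5.2, state that on-treatment hypoglycaemias count regardless of rescue, and replace the OC label with OR. Table 6.6: 1 defines OR for binary endpoints without picking one value per visit. OC-ROC would also serve if its visit rule is expressly waived, because SAP 6.7 does not assign these events to visits.
3. Add one sensitivity analysis of the same endpoint that counts events only up to the start of rescue, and state how patients without an event before rescue are coded. Requiring both analyses to agree before any claim would be a matter of preference and is not needed here.
4. In the same edit, reconcile two neighbouring differences on this endpoint: the full analysis set in SAP 7.5.2 against the treated set in Protocol 7.4.1, and counting up to drug stop in SAP 7.5.2 against drug stop plus 7 days in SAP 6.7.

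For the rescue handling itself (items 1 to 3), the cost is two wording changes and one extra run of an existing model, with no new data. Item 4 is further wording only. The downside is a possibly less favourable hypoglycaemia result.

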6.7 BASELINE, TIME WINDOWS AND CALCULATED VISITS

Definition of baseline

With regard to efficacy and safety endpoints, the term "baseline" generally refers to the last observed measurement prior to administration of any randomised study medication. Baseline daily basal insulin dose is derived from eCRF and is equal to the daily basal insulin dose at day of first study medication intake. If patients are treated by a combination of a fast-acting and basal insulin, only the proportion of basal insulin is used for deriving the baseline daily basal insulin dose. If that proportion cannot be derived, baseline daily basal insulin is set to missing.

If patients are treated with an intermediate type of insulin, then this dose is completely considered for daily basal dose.

Also, for metformin and AGI, baseline doses refer to the dose at day of first study medication intake.

Measurements taken prior to the first intake of randomised trial medication will be considered pre-treatment values. These pre-treatment values will be assigned to a visit according to the nominal visit number as recorded on the eCRF or as provided by the laboratory.

The date and clock time of the first study medication administration will be used to separate pre-treatment from on-treatment values.

The definition of screening for the analysis of concomitant therapies (CTs) is the time period from informed consent up to the first dose of trial medication.

Definition of on-treatment for analyses

Measurements taken after the first intake of randomised study medication will be considered on-treatment values if they have been obtained up to 7 days after study medication stop (inclusive) – this also holds for hypoglycaemia (efficacy endpoints) and hypoglycaemic adverse events (safety endpoints). The only exceptions are FPG [REDACTED] for which will be up to 1 day after drug stop (inclusive) due to reacting quicker. All on-treatment measurements will be assigned to the randomised trial medication for analyses.

Measurements taken after the end of the follow-up period after the last intake of trial medication will be considered post-trial values.

Visit windows for efficacy variables

On-treatment efficacy measurements will be assigned to visits based on time windows around the planned visit dates. These time windows are defined based on the planned number of days after the date of first administration of trial medication (this is at Visit 3).

The midpoint between two on-treatment visits defines the end of a time window, with the midpoint being included in the time window of the preceding visit. The end of the time window of the last on-treatment visit (EoT) is endpoint dependent (7 days after last intake for all variables except FPG [REDACTED] which are 1 day).

Table 6.7: 1 Time windows for on-treatment HbA_{1c} and FPG measurements scheduled for each on-treatment visit – Week 24

Visit number	Visit label	Planned days after randomisation	Planned days on treatment	Time window (actual days on treatment)	
				Start	End ^A
3	Baseline	0	1	NA	1 ^B
98 ^C	Week 24	168	169	149	Trial medication stop date + x ^D days
For Japanese Patients Only					
7	Week 24	168	169	149	176

^A In case of premature discontinuation of the trial medication a Visit 98 (end of treatment) has to be performed. If such a Visit 98 falls into the time window of a previous visit, measurements will be assigned to this previous visit. In this case the time window for the visit that includes Visit 98 will end x days after the trial medication stop date, including day x. The definition of x is endpoint specific, cf. [Table 5.3: 1](#)

^B Only values taken prior to the start of treatment with randomised trial medication can be considered baseline values. Time windows will be used for assignment of measurements to scheduled visits.

^C Only for non-Japanese patients.

^D cf. [Table 5.3: 1](#).

For examinations that are not planned at every on-treatment visit, the time windows will be defined according to the same algorithm, based on the midpoint between the planned visit day of such an examination.

Repeated and unscheduled efficacy measurements will be assigned to the nominal visits and listed in the subject data listings according to the time windows described above. Only one observation per time window (visit value / picked value) will be selected for analysis at an on-treatment visit – the value will be selected which is closest to the protocol planned visit day; except for last study drug intake. In case of last study drug intake, the value which is closest to the date of last study drug intake is chosen. If there are two observations which have the same difference in days to the planned day or if there are two observations on the same day, the earliest value will be used. If an observation is available on the last day of treatment, this observation will be preferably selected over any later observation that is still within the time window. If there are multiple values within the time window of the last visit,

including a value on the last day of drug intake, the value on the last day of drug intake is used as the value of the last visit.

Note: For LOCF imputation, the last observed on-treatment value will be carried forward, whether or not it was selected in the previous time window. Also for interpolation any valid values can be used, regardless of whether they were selected as visit values. For more details on LOCF refer to [Section 6.6](#).

For daily basal insulin the value at the visit will be determined as the last prescribed dose prior to the picked HbA1c value of the visit.

Visit windows will not be applied to hypoglycaemia or use of rescue therapy and events will not be assigned to visits. All on-treatment events will be considered in the analysis.

Visit windows for safety variables

Safety measurements will be assigned to the nominal visit as recorded on the eCRF or as provided by the laboratory. In general, visit windows will not be applied. However, for the Week 24 analysis, if a Japanese patient stops drug intake prior or at day 175 a residual period of 7 days will be added for safety analysis. If a Japanese patient does not stop drug intake prior day 176, no residual period is added for safety analysis at Week 24.

